1.1.3.3 Safety

Idalopirdine was safe and generally well tolerated in healthy subjects (young and elderly men and women) following multiple doses up to 300 mg/day with no clinical significant effects on vital signs, clinical laboratory tests or ECG parameters.

In the phase II study, 12936A, conducted in patients with AD, idalopirdine was safe and, with the exception of elevated transaminase values, well tolerated as adjunctive therapy to donepezil in patients with AD at a dose of 90 mg/day (30 mg TID) for 6 months.

In this study, the incidence of treatment-emergent adverse events (TEAEs) was slightly higher in the idalopirdine group (66%) than in the placebo group (59%). The most common adverse events, (occurring in >2 patients and with an incidence of more than 4% and with a >2 times higher incidence in patients treated with idalopirdine than in patients treated with placebo), were γ -glutamyltransferase increased, Alanine aminotransferase (ALT) increased, Aspartate aminotransferase (AST) increased, Dizziness, Headache, Aggression, and Vomiting.

The proportion of patients who withdrew due to TEAEs in this study was 15% in the idalopirdine group and 7.5% in the placebo group. The differential withdrawal was almost entirely due to elevated liver enzymes test values reported as TEAEs.

A total of 14 (9.7%) patients in the idalopirdine group and 13 (9.8%) patients in the placebo group had one or more serious adverse events (SAEs).

There were more patients in the idalopirdine group than in the placebo group who had AST, ALT and/or alkaline phosphatase (AP) values above the upper limit of normal (ULN) at some point during the study. There were no differences between the treatment groups in the incidence of total bilirubin level (TBL) above ULN. A total of 13 patients (all in the idalopirdine group) had AST or ALT values that were >2 times ULN. The elevated liver test values were seen around week 8. For all the 13 patients, the liver test values subsequently decreased towards the reference range. The mechanism behind these increased liver tests is currently unknown.

Except for liver tests, the changes from baseline for all clinical safety laboratory tests and ECGs showed, on average, small fluctuations without clinical relevance and with no trends over time or between the treatment groups.

In the two phase II studies conducted in patients with schizophrenia, idalopirdine was safe and well tolerated for up to 12 weeks.

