The investigator must review (initial and date) the results of the clinical safety laboratory tests as soon as possible after receipt of those results. Out-of-range values must be interpreted by the investigator with a comment of "not clinically significant" or "clinically significant" with a comment concerning the planned follow-up. Tests for clinically significant out-of-range values must be repeated, or an appropriate clinical follow-up must be arranged by the investigator and documented on the laboratory report, until the value has stabilised or until the value has returned to a clinically acceptable value (regardless of relationship to IMP). Any value that was out-of-range at the Completion or Withdrawal Visit and judged clinically

significant must be followed according to accepted medical standards for up to 4 weeks or until resolution of the abnormality, whichever comes first. Any out-of-range values, except for AST or ALT, followed after the last protocol-specified contact with the patient will be documented in the patient's medical records.

Patients with AST or ALT values >3 times ULN at the Completion or Withdrawal Visit should be followed until the values normalise or return to the Baseline I values or a diagnosis has been established (see section 8.7). The results must be recorded in the eCRF until the end of the study (see section 8.7).

Patients with repeat testing (within 48-72 h) showing AST/ALT >3 times ULN should follow "close monitoring" with:

- Repeating liver enzymes (AST, ALT, AP, γ GT) and serum bilirubin 2-3 times weekly. Frequency of re-testing can be decreased to once a week or less if abnormalities stabilise, or the patient is withdrawn and the patient is asymptomatic. The follow-up laboratory tests should preferably be taken at site and processed in the central laboratory. If this is not at all possible, local laboratories are accepted.
- Obtaining a more detailed history of symptoms and prior or concurrent diseases.
- Obtaining a history of concomitant drug use (including non-prescription medications and herbal and dietary supplement preparations), alcohol use, recreational drug use, and special diets.
- Ruling out acute viral hepatitis types A, B, C, D, and E; autoimmune or alcoholic hepatitis; non-alcoholic steatohepatitis; hypoxic/ischemic hepatopathy; and biliary tract disease.
- Obtaining a history of exposure to environmental chemical agents.

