16.9.3 Analysis of Liver Tests

In addition to the standard summary of clinical safety laboratory tests, the incidences of

- ALT/AST > 1x, 1.5x, 2x, 3x, 5x, 10x, 20x ULN
- TBL > 1x, 1.5x, 2x ULN
- AP > 1.5x, 2x ULN
- ALT/AST > 3xULN and TBL > 2xULN
- ALT/AST > 3xULN and TBL > 2xULN and AP \leq 1.5xULN
- ALT/AST > 3xULN and (TBL > 2xULN or INR > 1.5xULN) and AP \leq 1.5xULN

will be produced.

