11.3.3 Evaluation of Potential Drug-induced Liver Injury (DILI)

Signals of DILI post-Baseline II for the open label treatment period and post Baseline III for the open label treatment period with memantine will be assessed according to the FDA guideline¹, as well as by using additional criteria, as described below:

The number and percentage of patients post-Baseline II/Baseline III in the categories below for AST/ALT, and AST and ALT separately will be summarised:

Version: 1.0

- ULN < value ≤ 1.5 xULN
- $1.5xULN < value \le 2xULN$
- $2xULN < value \le 3xULN$
- $3xULN < value \le 5xULN$
- $5xULN < value \le 10xULN$
- $10xULN < value \le 20xULN$

LU Study Number: 14861B Trial Site Number: Study Level Pluto ID: CLI 00933680

Status: Final

• 20xULN < value

The number and percentage of patients post-Baseline II/Baseline III in the categories below for ALP and Bilirubin will be summarised:

- ULN<value ≤1.5xULN
- 1.5xULN< value <2xULN
- 2xULN< value ≤3xULN
- value >3xULN

In the summaries, each patient should be counted only once using the worst post-Baseline II/Baseline III assessment.

The cumulative number and percentage of patients post-baseline in the categories will also be summarised for each treatment period.

Number and percentage of patients fulfilling the joint criteria below post-baseline II/Baseline III will be summarised:

- (PEAK AST OR PEAK ALT>3xULN) AND PEAK BILI>2xULN AND PEAK ALP>1.5xULN
- (PEAK AST OR PEAK ALT>3xULN) AND PEAK BILI>2xULN AND PEAK ALP<1.5xULN
- PEAK GGT>200 (IU/L) without (PEAK AST OR PEAK ALT OR PEAK ALP>2xULN)
- Number and percentage of patients with a post-Baseline II /Baseline III value ≥5% for Beosinophils/leukocytes (ESOLE) will be summarised.

Evaluation of potential Drug-Induced Serious Hepatotoxicity (eDISH) will also be done by plots. Scatter plots of peak ALT/AST versus peak BILI in the treatment period (note that this means that the peak ALT/AST and the peak BILI may not occur at the same assessment timepoint). The values will be normalised by the ULN (unit xULN) and the X and Y-axes will be on log scale. The plot will include a reference line for ALT/AST values >3xULN, and a reference line for BILI values>2xULN. Four quadrants are defined by the reference lines, where the right upper quadrant being the most specific indicator for a drug's potential for causing serious liver injury (Hy's law quadrant). The plot will include number of patients in each quadrant.

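### SAP 11.3.3 sorts joint ALT/AST-and-bilirubin cases by period-maximum ALP, so a high ALP at another sample reclassifies a case with low ALP at the event, and exactly 1.5xULN falls in neither row

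*SAP*

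**What the plan says.** SAP 11.3.3 gives two joint criteria that differ only in the ALP term. The raised-ALP row (my label) is "PEAK AST OR PEAK ALT>3xULN) AND PEAK BILI>2xULN AND PEAK ALP>1.5xULN". The low-ALP row (also my label) is "PEAK AST OR PEAK ALT>3xULN) AND PEAK BILI>2xULN AND PEAK ALP<1.5xULN". Both apply after Baseline II or Baseline III, that is, within each treatment period.

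The joint criteria do not define peak, but the rest of the section points one way. The eDISH output is described as "Scatter plots of peak ALT/AST versus peak BILI in the treatment period", with the remark "note that this means that the peak ALT/AST and the peak BILI may not occur at the same assessment timepoint". The counting rule after the category lists is that "each patient should be counted only once using the worst post-Baseline II/Baseline III assessment". SAP 11.3.1 takes the worst liver value over all available assessments. Nothing ties the ALP value to the time of the ALT/AST and bilirubin rise.

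Protocol 16.9.3 lists the corresponding criterion as "ALT/AST > 3xULN and TBL > 2xULN and AP" at or below 1.5xULN, with no mention of peaks and no timing rule. It also lists ALT/AST >3xULN with TBL >2xULN and no AP condition. SAP section 17 declares one change from the protocol, to the C-SSRS summary.

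**The concern.** Taking the period maximum has opposite effects on the two kinds of condition. For ALT/AST >3xULN and bilirubin >2xULN, it can only bring patients in. For ALP below 1.5xULN, it can only take patients out. A single high ALP before or after the event, for whatever reason, is enough to reclassify a case whose ALP was low when ALT/AST and bilirubin were raised.

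The sampling plan adds to this. Under protocol 9.4.2, patients with ALT/AST confirmed above 3xULN have AST, ALT, AP, γGT "and serum bilirubin 2-3 times weekly", less often once values stabilise. Protocol 10.5 requires liver follow-up after withdrawal for raised AST or ALT. The patients at issue are therefore the ones with the most ALP samples.

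Safety is the primary objective, and protocol 1.1.3.3 names elevated transaminases as the exception to good tolerability in the phase II Alzheimer's study. A table that splits the joint cases by ALP should describe the event, not an unrelated sample.

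**Working it through.** The documents give no figure for this criterion, so there is none to reproduce. The check applies the rules as written to hypothetical patients.

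**Rules**

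- SAP raised-ALP row: max(ALT/AST) >3, max(bilirubin) >2, max(ALP) >1.5.
- SAP low-ALP row: the same first two terms, max(ALP) <1.5.
- Protocol limit read with peaks: the same first two terms, max(ALP) <=1.5. The peak reading is assumed here, because protocol 16.9.3 states no timing.
- eDISH quadrant: max(ALT/AST) >3, max(bilirubin) >2, no ALP term.
- Same-sample rule, for comparison: ALT/AST >3, bilirubin >2 and ALP <=1.5 at one sample.

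**Hypothetical patients (values in xULN).** A, B and C share a week 8 event with ALT 6, bilirubin 2.5 and ALP 0.9.

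- A: ALP 1.6 at week 20.
- B: ALP never above 1.2.
- C: peak ALP exactly 1.5, at week 12.
- D: ALT 4 at week 4, bilirubin 2.5 at week 12, ALP never above 1.0.

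| Patient | SAP low-ALP | SAP raised-ALP | Peak ALP <=1.5 | eDISH quadrant | Same sample |
|---|---|---|---|---|---|
| A | no | yes | no | yes | yes |
| B | yes | no | yes | yes | yes |
| C | no | no | yes | yes | yes |
| D | yes | no | yes | yes | no |

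**Reading the table**

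1. A and B have the same event. A's maximum ALP is 1.6 >1.5, so A is counted with raised ALP although ALP was 0.9 at the event.
2. C is in neither SAP row, since 1.5 is neither >1.5 nor <1.5. The protocol's <=1.5 would include C.
3. D enters the low-ALP row although the ALT and bilirubin limits were never exceeded at the same sample. The peak rule therefore also adds patients, and the net error of the row against a same-sample rule has no known sign.
4. All four are in the eDISH quadrant, which has no ALP condition.

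**Where the other sample could come from.** Protocol 5.4 requires withdrawal when ALT/AST >3xULN and bilirubin >2xULN, so A would not normally attend a scheduled week 20 visit. That value would have to come from continued liver follow-up. An earlier scheduled sample or a close-monitoring sample would have the same effect. SAP 11.3.3 does not say when the window for post-baseline liver values closes, so it is unclear whether follow-up samples taken after the last dose count.

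**The case against.** **No case disappears.** This is right. A patient who leaves the low-ALP row appears in the raised-ALP row, except at exactly 1.5xULN. The eDISH quadrant counts the patient whatever the ALP. SAP 11.3.3 also provides overlaid line plots for every patient with ALT/AST above 1xULN, and a dated listing of all liver values. With few cases, a reader could find the ALP at the event. That limits the harm, but the tabulated split stays wrong and has to be corrected by hand.

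**The protocol sets no timing rule.** Also right: protocol 16.9.3 is silent, and protocol 16.12 leaves detail to the SAP. Time matching is a better analysis choice, not something the protocol already requires. Only the boundary is a direct departure.

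**The boundary is trivial or a text slip.** It matters only at exactly 1.5xULN. The ALP/bilirubin category list in the same section also mixes < and <=, so a typing or PDF-reading error is possible. The sign should be checked against the source file, and correcting it costs nothing.

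Three stronger readings are tempting, and the documents do not support them.

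- A reader might infer that this row is the main liver count. The SAP uses the term Hy's law only for the eDISH quadrant and treats that quadrant as the most specific indicator.
- A reader might infer that raised ALP is an established finding on idalopirdine. Protocol 1.1.3.3 says only that there were more patients on the drug "who had AST, ALT and/or alkaline phosphatase (AP) values above the upper limit of normal (ULN) at some point during the study". That is a composite above 1xULN, and raised ALP is not among the common adverse events named there.
- A reader might put a percentage on the misclassification from a per-sample chance of high ALP and a number of samples. The documents give no such chance, repeated samples within one episode are not independent, and withdrawal under protocol 5.4 stops the remaining scheduled visits for concurrent cases.

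**Conclusion.** The concern holds as a classification error of limited consequence. As written, the low-ALP row undercounts patients whose ALP was at or below 1.5xULN at the event, and the raised-ALP row gains them. A peak of exactly 1.5xULN falls in neither row, against the protocol's <=1.5xULN and without declaration in SAP section 17. The documents do not allow the number of affected patients to be estimated, nor do they show that the overall liver conclusion would change.

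This rests on two readings: that peak in the joint criteria means the treatment-period maximum, as elsewhere in SAP 11.3.3, and that the < sign is as printed in the source. The correction is worth making because it is specific and inexpensive and concerns the primary, safety objective.

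**What to change.** In SAP 11.3.3:

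1. Restore <=1.5xULN in the low-ALP row, so that the two rows are exhaustive and agree with protocol 16.9.3.
2. Add a row that classifies on the ALP taken with the sample at which ALT/AST >3xULN occurs with bilirubin >2xULN, or on the ALP closest to it within a stated number of days.
3. Keep the peak-based rows as a supplement, labelled as such. They still serve patients whose ALT/AST and bilirubin peaks do not coincide.
4. Tabulate the protocol's row of ALT/AST >3xULN and TBL >2xULN with no ALP condition.
5. Define peak for the joint criteria, state which follow-up samples enter it, and record any remaining departure from protocol 16.9.3 in section 17.

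The data are already collected. The cost is SAP wording, a little programming, and two versions of the row, which need clear labels.

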11.4 Vital Signs and Weight

The PCS criteria for vital signs and weight are in Table 2.

An overview of the graphical presentations is provided in Panel 4.

Panel 4 Graphical Presentations for Vital Signs and Weight

Variable	Measure	Patient Selection	Line Plot
Weight	Absolute value	Patients with a post-Baseline II PCS Low Value Compared to Baseline I in the open label treatment period	V
Weight	Absolute value	Patients with a post-baseline II PCS Low Value Compared to Baseline II in the Open-label Treatment Period	V
Weight	Absolute value	Patients with a post-baseline III PCS Low Value Compared to Baseline I	$\sqrt{}$
Weight	Absolute value	Patients with a post-baseline III PCS Low Value Compared to Baseline III	V

11.5 ECGs

The PCS criteria for the ECG parameters are in Table 3.

An overview of the graphical presentations for the ECG parameters is provided in Panel 5.

LU Study Number: 14861B Pluto ID: CLI 00933680

Status: Final

Trial Site Number: Study Level

Version: 1.0

Page 21 of 48

Panel 5 Graphical Presentations for ECG Parameters

Parameter	Measure	Patient Selection	Line Plot
Heart ate	Absolute value	Patients with a post-Baseline II PCS value compared to Baseline I in the open label treatment period	V
Heart ate	Absolute value	Patients with a post-Baseline II PCS value compared to Baseline II in the open label treatment period	$\sqrt{}$
QTcF	Absolute value	Patients with a post-Baseline II PCS value compared to Baseline I in the open label treatment period	$\sqrt{}$
QTcF	Absolute value	Patients with a post-Baseline II PCS value compared to Baseline II in the open label treatment period	\checkmark
Heart rate	Absolute value	Patients with a post-Baseline III PCS value compared to Baseline I	$\sqrt{}$
Heart rate	Absolute value	Patients with a post-Baseline III PCS value compared to Baseline III	$\sqrt{}$
QTcF	Absolute value	Patients with a post-Baseline III PCS value compared to Baseline I	$\sqrt{}$
QTcF	Absolute value	Patients with a post-Baseline III PCS value compared to Baseline III	\checkmark

11.6 Columbia-Suicide Severity Rating Scale (C-SSRS)

For all visits, the C-SSRS was assessed using the Since Last Visit Version that collects information for a pre-specified, limited period.

The C-SSRS scores will be summarised (as described below) for open-label treatment period and open label treatment period with memantine for patients with at least one post-Baseline II/Baseline III, regardless of whether they had a Baseline II/Baseline III assessment.

Missing C-SSRS scores will not be imputed.

The C-SSRS items are described in Panel 6. Patients with *no suicidal ideation or behaviour* are those who answered "No" to all items for *suicidal ideation* and *suicidal behaviour*. For each evaluation (baseline II and post-baseline II for the open label treatment period, and baseline III, and post-baseline III for the open-label treatment period with memantine), the most severe event per patient related to *suicidal ideation* and *suicidial behaviour* will be summarised.

In the C-SSRS, *non-suicidal self-injurious* behaviour is captured as a different behaviour, and regarded independently of reported *suicidal ideation* and *suicidal behaviour* events. Positive responses to *non-suicidal self-injurious behaviour* will be summarised.

LU Study Number: 14861B Pluto ID: CLI 00933680

Status: Final

Trial Site Number: Study Level

Version: 1.0

Panel 6	C-SSRS Scores
I AIICI O	(-00110 0001 C

aCRF Item	Description		
	Suicidal Ideation		
CSSRS01	Wish to be dead		
CSSRS02	Non-specific active suicidal thoughts		
CSSRS03	Active suicidal ideation with any methods (not plan) without intent to act		
CSSRS04	Active suicidal ideation with some intent to act, without specific plan		
CSSRS05	Active suicidal ideation with specific plan and intent		
	Suicidal Behaviour		
CSSRS25	Preparatory acts or behaviour		
CSSRS23	Aborted attempt		
CSSRS21	Interrupted attempt		
CSSRS18	Non-fatal suicide attempt		
CSSRS27	Completed suicide (only applicable for the post-baseline assessments)		
	Self-Injurious Behaviour Without Suicidal Intent		
CSSRS20	Non-suicidal, self-injurious behaviour		

For patients with any post-baseline II/baseline III suicidal behaviour (C-SSRS scores of 6 to 10) or ideation (C-SSRS scores of 1-5), listings will be prepared including all C-SSRS scores; C-SSRS scores related to suicidal behaviour or ideation will be flagged.

12 Pharmacokinetic/Pharmacodynamic Analyses

Plasma concentrations of idalopirdine and memantine will be summarised descriptively for the APTS2 in the open-label treatment period with memantine.

13 Health Economic Analyses

The health economic assessments conducted during the open-label treatment period (RUD Lite, EQ-5D-3L and Dependence scale) in the open-label will be summarised by lead-in study. For the open label treatment period, absolute scores, change from Baseline I scores, and change from Baseline II will be summarised by visit week. The summaries of absolute scores and change from Baseline I scores will include data from the lead-in study and the open-label treatment period.

For the open label treatment period with memantine, absolute score and change from Baseline III in MMSE total score will be summarised by visit week.

14 Interim Analyses

No interim analyses planned.

Page 23 of 48 Trial Site Number: Study Level

LU Study Number: 14861B Pluto ID: CLI_00933680 Status: Final

Version: 1.0

15 Sample Size Considerations

Open-label treatment period:

The study will include eligible patients who have completed Visit 7 (Completion Visit) of the lead-in studies. Assuming a completion rate of 85% and that approximately 85% of these are eligible and complete the extension study, this results in a total of approximately $(3x310 + 3x280) \times 85\% \times 85\% \approx 1280$ patients completing this study.

Open-label treatment period with memantine (sub-study):

With a sample size of n=100 the upper 1-sided 90% confidence limit for 0 to 10 AEs observed is:

Number of AEs observed	0	1	2	3	4	5	10
Upper 1-sided CI for AE incidence	2.3%	3.9%	5.3%	6.6%	7.9%	9.1%	15.0%

This is regarded as sufficient accuracy for evaluating safety and tolerability.

16 Data and Analysis Standards and Statistical Software

The data will be collected and analysed in accordance with the Lundbeck standards specified in Lundbeck SDTM, Version 3.1.2 or later, SADs, Version 5.1 or later, and TGML, Version 7.0 or later.

The statistical software used will be SAS®, Version 9.4 or later.

17 Changes to Analyses Specified in the Protocol

C-SSRS will be summarized as worst case per treatment period rather than worst case per visit. However, all C-SSRS results for the study will be listed for those patients that experience any suicidal ideation or behaviour.

18 Details on Data Handling

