9.4.7 Columbia Suicide Severity Rating Scale (C-SSRS)

C-SSRS¹⁸ done at Visit 7 (Completion Visit) of the lead-in study will be transferred and will not be repeated at the Baseline II Visit.

For patients continuing into the open-label treatment period with memantine (substudy), assessments and procedures done at Visit 6 in the open-label treatment period (initial 28-week period) are the same as the Baseline III Visit.

The C-SSRS is a semi-structured interview developed to systematically assess suicidal ideation and behaviour of patients participating in a clinical study. The C-SSRS has 5 questions addressing suicidal ideation, 5 sub-questions assessing the intensity of ideation, and 4 questions addressing suicidal behaviour. Different versions of the scale are available: in this study the "Since last visit" version will be used at all visits. An experienced clinician can use the CSSRS after a short training session. It takes approximately 5 minutes to administer and rate the C-SSRS.

The C-SSRS should be rated by a neurologist, geriatrician, psychiatrist or (neuro-) psychologist involved in clinical practice. Any exceptions must be discussed and approved by a Lundbeck Scales Manager.

Only raters who have been trained and certified are allowed to rate patients in study 14861B. The documentation of training issued during the lead-in study covers the extension study 14861B and no additional documentation will be re-issued for existing raters.

New raters joining the study will be trained and certified by ePharmaSolutions using the same certification procedure as in the lead-in study. For each individual patient, the same certified rater should rate the patient throughout the study. In case of unforeseen circumstances, certified back-up raters should be available throughout the study.

Exceptional situations must be discussed and approved by the Scales Manager.

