16.9.2 Analysis of Other Safety Endpoints

Clinical safety laboratory tests, vital signs, weight and ECG parameters will be summarised by visit and last post baseline assessment in the treatment period. For the open-label treatment period (initial 28-week period), the summaries will be presented using data from both the lead-in study and the open-label treatment period (initial 28-week period).

Potentially clinically significant (PCS) values will be flagged and summarised.

If relevant, individual patient profile plots will be generated for selected parameters, using data from both the lead-in study and the extension study.

C-SSRS will be summarised by visit. For the open-label treatment period (initial 28-week period), the summaries will be presented using data from both the lead-in study and the open-label treatment period (initial 28-week period).

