18.1 Definition of Baseline

The Baseline I value will be defined as the value captured either at the Screening Visit or the Baseline Visit of the lead-in study, whichever comes later.

Unless otherwise specified, the Baseline II Visit is the same as the Completion Visit (Visit 7/Week 24) in the lead-in studies (14861A and 14862A).

LU Study Number: 14861B Trial Site Number: Study Level Pluto ID: CLI 00933680

Baseline III is the same as the Completion Visit (Visit 6/Week 28) of the open-label treatment period.

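### The C-SSRS summary sets a single-visit baseline beside a worst case over 24 or 28 weeks, so the post-baseline percentage is expected to be higher even if risk has not changed

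*SAP*

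**What the plan says.** **Instrument.** SAP 11.6 states that at all visits "the C-SSRS was assessed using the Since Last Visit Version that collects information for a pre-specified, limited period". Protocol 9.4.7 likewise applies this version at every visit, and the lead-in completion rating is carried over as Baseline II.

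**Baselines.** Each is a single visit. SAP 18.1 says that "the Baseline II Visit is the same as the Completion Visit (Visit 7/Week 24) in the lead-in studies" and that "Baseline III is the same as the Completion Visit (Visit 6/Week 28) of the open-label treatment period".

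**Summary.** SAP 11.6 reports the most severe event per patient under two evaluations in each period: "For each evaluation (baseline II and post-baseline II for the open label treatment period, and baseline III, and post-baseline III". SAP section 17 declares the change from the protocol: "C-SSRS will be summarized as worst case per treatment period rather than worst case per visit".

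**Protocol.** Section 16.9.2 planned otherwise: "C-SSRS will be summarised by visit". For the initial period it also commits to presenting lead-in and open-label data together. SAP 11.6 names only Baseline II onwards, and SAP section 17 does not mention that the lead-in data drop out of the summary.

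**Listings.** SAP 11.6 and section 17 provide a listing of all C-SSRS scores for patients with any ideation or behaviour.

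**Purpose.** Protocol 3.2 says the substudy design lets safety and tolerability be compared in the same patient before and after memantine is added.

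**The concern.** A since-last-visit rating can only pick up events in the interval it covers. The baseline entry covers one such interval; the post-baseline entry takes the worst of four or five. The longer entry has more chance to contain an event, whatever the drug does.

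Safety is the primary objective in both periods and is assessed descriptively, so the displayed percentages are the evidence. A rise from baseline to post-baseline could be read as suicidality emerging on idalopirdine 60 mg or after memantine was added. The plan gives no matched window, no rate per time covered and no caution on interpretation for this scale.

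**Working it through.** The documents give no C-SSRS figure to reproduce, so the check builds the look-back lengths from the visit schedule and asks what unchanged risk would produce.

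**Look-back lengths** (nominal days, Protocol Panels 2 and 3)
- Baseline III: Visit 5 (day 140) to Visit 6 (day 196) = 56 days = 8 weeks.
- Post-Baseline III: Visits 8-11, day 196 to day 364 = 168 days = 24 weeks. Intervals are 4, 4, 4 and 12 weeks.
- Post-Baseline II: Visits 2-6, day 0 to day 196 = 28 weeks. Intervals are 4, 4, 4, 8 and 8 weeks.
- Baseline II: the time since the previous lead-in C-SSRS. The lead-in schedule is not in the documents; 4 to 12 weeks is assumed.

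**Constant risk, independent intervals, full follow-up.** Let p be the probability of a positive rating in the baseline window and k the ratio of post-baseline to baseline look-back. Then P(post) = 1 - (1 - p)^k. The value of p is not given; 1% is used for illustration.

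| Comparison | k | P(post) at p = 1% | Ratio |
|---|---|---|---|
| Substudy, 8 vs 24 weeks | 3 | 1 - 0.99^3 = 2.97% | 2.97 |
| Initial period, 12 vs 28 weeks (assumed) | 2.33 | 2.32% | 2.32 |
| Initial period, 8 vs 28 weeks (assumed) | 3.5 | 3.46% | 3.46 |
| Initial period, 4 vs 28 weeks (assumed) | 7 | 6.79% | 6.79 |

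For p from 0.5% to 5% the substudy ratio runs from 2.99 down to 2.85. In counts, the substudy example is 1 patient against about 3 in 100. With the planned 1280 completers of the initial period it is about 13 at baseline against about 30, 44 or 87 for assumed intervals of 12, 8 or 4 weeks.

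**Clustering in the same patients.** If some patients are persistently at higher risk, the inflation shrinks. With a gamma frailty of variance v, P(post) = 1 - (1 + vHk)^(-1/v), where H = ((1 - p)^(-v) - 1)/v. At p = 1% and v = 100, H = (2.732 - 1)/100 = 0.01732. The substudy value is 1 - (1 + 1.732 × 3)^(-0.01) = 1.81%, a ratio of 1.8. For the initial period the ratio is 1.6, 1.9 or 2.5 for intervals of 12, 8 or 4 weeks. It reaches 1 only if the same patients are positive at every visit.

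**Selection before baseline.** Exclusion criterion 13 (initial period) and exclusion criterion 16 (substudy) in Protocol 5.3 bar patients with ideation items 4 or 5, or suicidal behaviour, on the C-SSRS within 12 months. Protocol 5.4 withdraws such patients during treatment. In these categories the pre-baseline entry is near zero by design, whatever its look-back length. The look-back effect therefore bears mainly on ideation items 1-3.

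**With the preceding period as comparator.** For the APTS, 24 weeks of lead-in against 28 weeks gives an expected ratio of about 28/24 = 1.17. For APTS2, 28 weeks (Visits 2-6) against 24 weeks gives about 24/28 = 0.86.

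**The case against.** The best defence is that this is an untested descriptive table. SAP 11.6 defines no change score, shift table or emergent-suicidality endpoint, and the change from the protocol was declared together with full listings. Lead-in groups share the same nominal post-baseline window, so comparing them is not affected by the mismatch. In a substudy of 100, the example is one patient against three, each with every score listed, so a reviewer can see when each event arose. All of this stands and limits the weight of the point. It does not remove it, because listings leave the summary percentages uncorrected and Protocol 3.2 invites the before/after reading.

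Three stronger readings are tempting but not supported:
- A reader might infer that a rise is guaranteed. It is an expectation under unchanged risk. Persistent ideation in the same patients and early withdrawal both reduce it.
- A reader might infer that the protocol's by-visit table would have compared like with like. The schedule gives intervals of 4, 4, 4, 8 and 8 weeks, then 4, 4, 4 and 12. The step from Visit 10 to Visit 11 is itself threefold.
- A reader might infer that matching the windows would remove any artificial rise. For ideation items 4-5 and behaviour it would not, because the entry and withdrawal criteria select those patients out beforehand.

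**Conclusion.** The mismatch is in the current text: 8 against 24 weeks in the substudy, fixed by the documents, and one lead-in interval against 28 weeks in the initial period. With unchanged risk the post-baseline percentage is expected to exceed baseline by up to about threefold in the substudy. That upper figure assumes independent intervals and full follow-up; with strong clustering it is about 1.8-fold, and early withdrawal lowers it further. For the initial period the ratio is about 2.3 to 7, resting on an assumed last lead-in interval of 12 down to 4 weeks.

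This is a presentation fault in a descriptive safety table, not a bias in any test or in contrasts between lead-in groups. It matters because it distorts the within-patient before/after reading that the protocol intends, chiefly for ideation items 1-3. It should be corrected.

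**What to change.** In SAP 11.6, replace or supplement the single-visit baseline entry with the worst post-baseline rating over the preceding treatment period:
- APTS: the 24-week lead-in treatment period, by lead-in arm. Protocol 16.9.2 already commits to using lead-in data.
- APTS2: Visits 2-6 of the initial period.

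Add two footnotes. The first gives the look-back length of each column. The second says that the entry and withdrawal criteria remove patients with ideation items 4-5 or suicidal behaviour before each baseline, so an apparent rise in those categories remains and should be read from the listings. Show the number of patients rated in each column, since SAP 11.6 also counts patients who have no baseline rating.

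If a by-visit table is used instead, state its unequal intervals (4, 4, 4, 8, 8 weeks and 4, 4, 4, 12 weeks).

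The cost is SAP wording and one revised table shell. No new data, visits or procedures are needed. The remaining weakness is the selection in the severe categories, which the footnote discloses but cannot remove.
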